4 STUDY DESIGN

4.1 OVERALL DESIGN

The null hypothesis of the SF Study is that subject's perceived hearing aid benefit using *Vibe SF* hearing aids is inferior to Silk 1X HCP fit hearing aids, and the alternative hypothesis is that subject's hearing aids benefit using *Vibe SF* hearing aids is non-inferior to that using Silk 1X HCP fit hearing aids.

A prospective, randomized controlled, adaptive design, non-inferiority, pre-market and NSR device study. The first 12 subjects will participate in the cross-over design, after which an interim analysis of a nuisance parameter will be conducted to evaluate whether there is an interaction effect. If there is, the design will be changed to parallel-arm, the sample size will be increased to 50, and the remaining 38 subjects will

receive just one fitting (to which they are randomized). If there is no significant interaction effect, the 28 subjects originally planned will complete the cross-over design.

Cross-over design: 28 subjects

At the final Visit 3 the order of evaluating hearing aids (Vibe SF /Silk 1X HCP fit) will be randomized to ensure double-blinding to minimize subject and HCP bias while conducting the QuickSIN and REM laboratory assessments.

Parallel-arm design: 50 subjects

For 38 subjects, the final visit will be at Visit 2 and the REM and QuickSin will be tested with the Field Test 1 device. 12 subjects will complete the final visit where the order of evaluating hearing aids (Vibe SF /Silk 1X HCP fit) will be randomized to ensure double-blinding to minimize subject and HCP bias while conducting the QuickSIN and REM laboratory assessments.

This study has two fitting strategy groups, *Vibe SF* and HCP fit. In subjects who participate in the cross-over design, each subject is in each fitting strategy group for 14 days, 5-day washout period after cross over and total subject study intervention duration is 7 weeks. In subjects who participate in the parallel-arm design, each subject is in just one fitting strategy for 14 days. There is no washout period, and no cross-over to the other fitting.

A single US University hearing aid research clinic will be the clinical site in this study. The investigational site serves 15% Native American, 5% African American and other diverse American population.

The name of the self-fitting air conduction hearing aid is *Vibe SF*. The *EasyFit* web application is intended to support the SF strategy of the *Vibe SF*. The *Vibe SF* strategy is being evaluated in this study.

To address a possible significant interaction effect, a sample size re-estimation based on the nuisance parameter: interaction term will be conducted after 12 subjects have completed Visit 3.

4.2 SCIENTIFIC RATIONALE FOR STUDY DESIGN

Research of self-fitting hearing aids is limited, there is only one current published SF validation study done by the predicate device from Bose. Today the landscape of the hearing industry is changing quickly due to the rapid advancement of amplification technology as well as changes in federal regulations of the hearing aid market.

The sponsor does not know, before initiating the study, whether the interaction between treatment and order is significant. It is the company's belief that an interaction effect is unlikely because many studies in the hearing aid literature use cross-over designs, and none mention a significant interaction effect. Therefore, the company prefers not to start with the assumption that it is necessary to conduct a parallel-arm trial. To address concerns about a possible interaction effect, the sponsor proposes to address this potential problem by using an adaptive design: changing to a parallel-arm design based on a nuisance parameter. The nuisance parameter is the interaction term.

It is important to differentiate between traditional hearing aids and SF hearing devices, not only in terms of device characteristics but also in terms of expected subject outcomes. Also, it is important to differentiate the devices that produce the best patient outcomes across various listening situations. Therefore, there is a scientific need to develop an evidence base with well-controlled studies in relation to SF hearing aids.

Assessing the non-inferiority of the SF hearing to HCP fit hearing was the chosen study design because HCP counseling on hearing loss has been established in research as being best practice. In the rapidly changing distribution of model of hearing healthcare, it may become more likely a person with perceived hearing loss will utilize a self-fitting method as an introduction to hearing care. In the absence of a best practices model involving the HCP, it is necessary to verify that a hearing aid user's first experience with amplification is such that core expected benefits are met with a self-fitting approach. This does not prevent future intervention with a HCP. Rather, a self-fitting approach to amplification should provide noticeable benefit comparable to that of best practices to overcome key challenges of hearing loss directly related to reduced audibility. In this way, the new hearing aid wearer can begin experiencing benefits of amplification and develop a positive acceptance of hearing healthcare.

It cannot be expected for a SF hearing aid to be superior as the advantages of the SF lie in accessibility and ownership not the fitting-process itself. However, in the best interest of the subjects it has to be ensured that the hearing aid fitting is not inferior to that what they would get from the standard alternative, i.e., being fitted by a HCP.

4.3 END OF STUDY DEFINITION

28 subjects are considered to have completed the study when they have completed all phases of the study including the last visit shown in the SoA, Section 1.3.

In the event an additional 22 subjects are enrolled due to detection of significant interaction effect, these are considered to have completed the study when they have completed Visit 2. Refer to SoA, Section 1.3.

The end of the study is defined as the last subject's (minimum 24th subject, maximum 50th subject) completion of the last visit shown in the SoA in the study.

5 STUDY POPULATION

5.1 INCLUSION CRITERIA

In order to be eligible to participate in this study, an individual must meet all of the following criteria:

- Adults 18 years of age or older,
- Self-perceived mild to moderate hearing impairment,
- Signed informed consent form (ICF),
- Fluent in English listening and reading comprehension,

- With or without prior experience with hearing aids. At least four subjects and maximum 30% of the total number of subjects enrolled in this study will have prior hearing aid experience.
- Measured audiogram with at least four of the test frequencies 500 Hz, 1000 Hz, 2000 Hz, 3000 Hz, and 4000 Hz within fitting range of *Vibe SF* hearing aid (See Figure 1 below).

[figure not shown]

Figure 1. The colored area shows the fitting range of *Vibe SF* Hearing aids with the use of vented click sleeves; the hearing loss of the subjects should fall within that area.

5.2 EXCLUSION CRITERIA

An individual who meets any of the following criteria will be excluded from participation in this study:

- Silk 1X (HCP fit)/ *Vibe SF* hearing aids do not fit into the person's ears with any of the offered silicone 'Click Sleeves' instant ear tips.
- Abnormal conditions:
 - Severe hearing loss or deafness in at least one ear.
 - A steep decline in hearing ability within the last 90 days in one or both ears.
 - Active discharge within the last 90 days.
 - Dizziness.
 - A visible deformity of the ear.
 - Pain, or discomfort in the ear, or significant ear wax accumulation.
 - Audiometric air-bone gap equal to or greater than 15 decibels at 500 hertz Hz, 1,000 Hz, and 2,000 Hz.

5.3 SCREEN FAILURES

Screen failures are defined as subjects who consent to participate in the study but are not subsequently entered in the study. A minimal set of screen failure information is required to ensure transparent reporting of screen failure subjects, to meet the Consolidated Standards of Reporting Trials (CONSORT) publishing requirements and to respond to queries from regulatory authorities. Minimal information includes demography, screen failure details, eligibility criteria, and any serious adverse event (SAE).

5.4 STRATEGIES FOR RECRUITMENT AND RETENTION

The study will enroll a minimum of 28 US subjects and a maximum of 50 US subjects, 18 years of age and older, inexperienced or experienced (minimum 4, maximum 30% in total) hearing aid users with perceived mild-to-moderate hearing impairment that will be screened to confirm that s/he has bilateral sensorineural hearing loss.

Potential subjects will be recruited locally by outreach at the investigator site (i.e., a single US University hearing aid research clinic), local advertisements, social media advertisements and professional recruiting service. Advertisements will be reviewed and approved by the IRB to assure that they are not unduly coercive and does not promise a certainty of cure beyond what is outlined in the consent and the protocol. No claims will be made, either explicitly or implicitly, that the device is safe or effective for the purposes under investigation, or that the test article is known to be equivalent or superior to any other device. FDA considers direct advertising for study subjects to be the start of the informed consent and subject selection process.

Study subjects will be reimbursed for travel expenses for each clinic visit not to exceed \$50/visit.

In case a subject withdraws from the clinical investigation the subject will receive transport compensation covering the number of times he/she has visited the investigation site during the clinical investigation.

As reimbursement for their time in filling out the EMA surveys and wearing the hearing aids during Field Test 1 & 2, and their testing time during Visit 1, 2, and 3, a total of US\$175 will be paid out to 28 subjects as outlined below:

Table 2. 28 Subjects: cross-over design

SCHEMA	Time	Amount	Payment
Screening	15 minutes	0	
Visit 1	60 minutes	15	
Field Test 1	14 days	40	55
Visit 2	60 minutes	15	
Field Test 2	14 days	40	55
Visit 3	120 minutes	65	65
TOTAL		US\$175	US\$175

Table 3. 50 Subjects: parallel-arm design

12 Subjects

SCHEMA	Time	Amount	Payment
Screening	15 minutes	0	
Visit 1	60 minutes	15	
Field Test 1	14 days	40	55
Visit 2	60 minutes	15	
Field Test 2	14 days	40	55
Visit 3	120 minutes	65	65
TOTAL		US\$175	US\$175

38 Subjects

[figure not shown]
SCHEMA	Time	Amount	Payment
Screening	15 minutes	0	
Visit 1	60 minutes	15	
Field Test 1	14 days	40	55
Visit 2	60 minutes	15	
TOTAL		US\$70	US\$70

6 STUDY INTERVENTION**6.1 STUDY INTERVENTION(S) ADMINISTRATION****6.1.1 STUDY INTERVENTION DESCRIPTION**

The investigational device *Vibe SF* hearing aid is a NSR medical device that does not pose a significant risk to human subjects based on its intended use. The *Vibe SF* is intended to amplify sound for individuals 18 years of age or older with perceived mild to moderate hearing impairment. It is adjusted by the user to meet the user's hearing needs through software tools. The device is intended for direct-to-consumer (DTC) sale and use without the assistance of a hearing care professional (HCP). *Vibe SF* is intended to be sold as a binaural set and the *Vibe SF* strategy is intended to be binaural. The investigational device immediate package shall bear a label with the following statement: "CAUTION—Investigational device. Limited by Federal (or United States) law to investigational use."

The instant fit in-the-ear (ITE) style *Vibe SF* hearing aid uses silicone 'Click Sleeves' which are instant ear tips in four different sizes to provide comfort and secure device placement within the ear canal. The click sleeves are also used on the global market together with the Signia Silk Xperience devices (e.g., Silk 1X HCP fit control device) and other Signia products.

All hearing aids in the study are provided in black housing and marked with 'R' and 'L', for right and left side respectively, as displayed in Figure 2.

- ① Click Sleeve
- ② Microphone
- ③ Battery door (on/off switch)
- ④ Removal cord
- ⑤ Side and orientation indicator: arrow shall point upwards

Figure 2. Drawings of the *Vibe Air SF* hearing aid: a) left side housing marked 'L', b) right side housing marked 'R', c) click sleeve, microphone, battery door, removal cord and side/orientation indicator.

The *EasyFit* web application is used to guide the user through the *Vibe SF* procedure and to set audiological gain parameters and preferred settings on the *Vibe SF*. *EasyFit* web application is designed to function in standard browsers of a user's compatible smartphone or tablet device. Access to the internet is required when using *EasyFit* web application during the SF procedure, fine-tuning and use of volume control.

Through the *Vibe SF* hearing aid, the *EasyFit* web application will present several sets of 2 or 3 tones to the subject for hearing ability profiling. Within such a test-tone-set all tones have the same frequency, but they differ in intensity level. Depending on the extent of hearing loss, the user will hear all, some or none of the presented tones. *EasyFit* web application will ask the user to enter the number of tones s/he hears. A selection of screen shots of the fitting process with the *EasyFit* web application are shown in Figure 3.

EasyFit web application can activate 4 different "clusters" in the hearing aid. "Clusters" in this context means different hearing aid settings. Those settings are the same with respect to hearing aid features, e.g., noise reduction etc., but they differ in frequency dependent gain, compression and MPO (maximum power output). *EasyFit* uses the result of the profiling procedure to select and activate the cluster and master gain setting that is most suitable for the user. In case of an asymmetrical hearing loss the cluster can differ across sides. A short additional test ensures the overall gain is comfortable and balanced between the left and right ears. After the fitting is completed, the user may further use *EasyFit* to fine-tune the hearing aid settings during daily use.

2. Hearing profile check

Now we will identify your hearing profile.

We will start with your left ear. You will hear a number of beeps. On the next screen please:

- Count the number of beeps
- Enter how many beeps you have heard
- Enter "0" if you did not hear any beep
- Click on "Replay" to hear the beeps again
- Take your time!

LEFT

Playing...

Continue

2. Hearing profile check

LEFT

Count how many beeps you hear.

How many beeps did you hear?

0 1 2 3

Replay

Good job!

You finished your LEFT ear.

Let's continue with your RIGHT ear.

Continue

Hints

Sometimes it may be difficult to hear the beeps. To make it easier for you please do the following:

- Go to a quiet environment
- Put the phone in front of you on a table
- Ensure that you do not cover the speaker of the phone with your hand
- Listen carefully and count the beeps
- Enter how many beeps you have heard
- Enter "0" if you did not hear any beep
- If you are not sure, click on "Replay" to hear the beeps again
- Take your time

Try Again

2. Hearing profile check

You have completed the Hearing Profile Check successfully! Please apply your personalized settings now.

This will take a few seconds.

Adjust Loudness

In the next step, you can adjust the loudness to a level that feels comfortable to you. Please have a conversation with another person.

Adjust Loudness

Loudness

Please have a conversation with another person. Adjust the level of each side until the other person sounds pleasant and is easy to understand.

Done

Figure 3 Selection of draft screenshots of hearing ability profiling in the *EasyFit* web application.

The control hearing aid device, Signia Silk Xperience, has been commercially available in the U.S. as a Class II 510(k)-exempt medical device since July 2020 in five models: Silk 7X, Silk 5X, Silk 3X, Silk 2X and Silk 1X. The performance levels for each model differ in the embedded software configuration but use identical hardware. The Silk 1X model will be fitted to the individual hearing thresholds by an HCP as per standard clinical care. The Connexx Fitting Software will be used to fit NAL-NL2 prescriptive target verified by probe-mic REM. The Connexx programming software allows the HCP access to certain programming parameters that are not accessible in the *Vibe SF* using *EasyFit*. Parameters that the HCP can adjust in the *Silk 1X* fitting are 8 adjustable gain and compression handles, Frequency Compression, Feedback cancellation (off, min, max). *Silk 1X* does support multiple programs, however only one single program (titled: universal program) will be used.

6.1.2 NONSIGNIFICANT RISK DETERMINATION

The Sponsor has determined that both the study and device are non-significant risk, based on the risk profile of this non-invasive device (see Appendix I), and a review of the Code of Federal Regulations definitions and rules regarding significant risk devices. The following rationale is cited as determination of non-significant risk:

The device does not meet the four elements of the definition for a significant risk device per 21 CFR 812.3, part (m) in that the device does not pose significant risk to the subject and is not an implant, does not support or sustain human life, and is not of substantial importance for diagnosis, curing, mitigating, preventing impairment to human health or treatment of ESRD patient. The risk assessment by the Sponsor concludes that the device poses minimal risk to the subject.

In Appendix I is a summary of the test validation studies.

6.1.3 INVENTORY AND DISPENSING

Investigator site will store the hearing aids in a locked room and cabinet. Only the designated staff at the investigator site will conduct the randomization and blinding coding and store randomized devices according to the sites working procedure. Only the designated staff is able to retrieve and directly give/ship out to subjects directly the randomized/blinded hearing aids. HCP may not be a designated staff to conduct randomization, blinding coding, storage, shipment or direct retrieval from storage of the devices to the subjects at Visit 3.

6.2 PREPARATION/HANDLING/STORAGE/ACCOUNTABILITY

6.2.1 ACQUISITION AND ACCOUNTABILITY

Sponsor will deliver the hearing aids to the investigation site before the first subject is enrolled in the study.

If for any reason devices need to be returned to the sponsor, investigator site will be provided with handling instructions at the study site initiation visit.

Return of all devices will be picked-up by the sponsor at the close out monitoring visit at the investigation site.

6.2.2 FORMULATION, APPEARANCE, PACKAGING, AND LABELING

6.2.2.1 INVESTIGATIONAL DEVICE: VIBE SF

Legal Manufacturer of the *Vibe SF* hearing aids is WSAUD A/S, [name]. Manufactured for Vibe Hearing, [name]

The investigational device will come in a hearing aid case placed in a cardboard box together with a pack of batteries, a cleaning brush, cleaning cloth and click sleeves sizes XS, M and L. The hearing aid case will contain left and right hearing aid with the click sleeve size S attached. See also Figure 3.

The investigational device will be handed out together with the Safety and Maintenance Information, a Quick start guide and a Quick start card.

[figure not shown]
Figure 3. Content enclosed in the *Vibe SF* cardboard box

The Cardboard box will bear the following information:

CAUTION Investigational device. Limited by Federal (or United States) law to investigational use.

Content: Jewel case with 2 hearing aids, silicone click sleeves in 4 sizes (XS, S, M & L), 6 batteries size 10, and cleaning tools.

Warning: For adults 18 years and older with mild to moderate hearing loss. Contact your primary care provider before using this product if you currently experience any of these conditions: (1) Severe hearing loss or deafness in at least one ear. (2) A steep decline in hearing ability within the last 90 days in one or both ears. (3) Active discharge within the last 90 days. (4) Dizziness. (5) A visible deformity of the ear. (6) Pain, or discomfort in the ear, or significant ear wax accumulation.

This NSR device study complies with the abbreviated IDE requirements set forth in (§812.2(b)). Therefore, the *Vibe SF* is labeled in accordance with §812.5.

The labeling of our investigational device does not contain any false or misleading statements nor imply that the device is safe or effective for the purposes being investigated.

[figure not shown]
Detailed information on device labeling is in Appendix II.

6.2.2.2 CONTROL DEVICE: SILK 1X

Legal Manufacturer of the Silk 1X hearing aids is Signia GmbH, [name]

The control device will come in a standard hearing aid jewel case enclosed in a cardboard box with the following information:

Brand: Signia

Signia GmbH
[name]
[name]

The investigational Site will be provided with Click Sleeves Size XS, S, M and L and Batteries in standard packaging to hand out to the participants during standard-of-care fitting at Visit 1 and Visit 2.

6.2.3 PRODUCT STORAGE AND STABILITY

Devices should be stored in their designated jewel cases or appropriate trays or boxes. Temperature for storage should be between 10 to 40 °C (50 to 104 °F). Relative humidity should be 10 to 80% and Atmospheric pressure 700 to 1060 hPa.

6.2.4 PREPARATION

Randomization coding and blinding coding need to be done in advance by the designated investigational site staff. The designated site staff must also set up their inventory so that they are able to track, store, deliver and retrieve the properly randomized and blinded devices designated to the subject at the time of their study visits and when shipping out devices for Field Test 2.

6.3 MEASURES TO MINIMIZE BIAS: RANDOMIZED TREATMENT ORDER AND BLINDING

To avoid order effect of evaluating *Vibe SF* strategy and *Silk 1X HCP fit* strategy, a balanced randomization list will be generated using approved statistical software. A computer-generated pseudo-random-number list will be used for assigning the treatment order. Assignments will be made either by sealed envelope or provided real-time on the sponsor's electronic database capture (EDC) website on a protected page. New hearing-aid users and experienced hearing-aid users will be distributed evenly in the two randomized groups.

Cross-Over Design: Minimum 12, Maximum 28 subjects

At the final visit (Visit 3), the order of testing the experimental and reference devices will be randomized for the QuickSIN and REM lab tests. Randomization will be handled by a designated person not otherwise involved in the study.

During each of the following performance measures, QuickSIN and REM, at Visit 3 when the subject is using the *Vibe SF* and *Silk 1X HCP fit* hearing aids, the identity of the *Vibe SF* and *Silk 1X* will be double blinded to the subject and assessor. An assistant other than the HCP will help secure double blinding during the lab assessments by handling the blinding codes, storing, retrieving and presenting the appropriate hearing aids for evaluation.

During Field Tests 1 and 2 use, blinding is not possible since the option of self-finetuning or finetuning visits to the HCP reveals the device under investigation.

6.4 STUDY INTERVENTION COMPLIANCE

A follow-up call made by investigation site staff to subjects within the first 3 days of their Field Test 1 and Field Test 2 will act as a check that they are wearing their hearing aids and that the EMA data collection is being completed and functioning properly.

7 STUDY INTERVENTION DISCONTINUATION AND SUBJECT DISCONTINUATION/WITHDRAWAL

7.1 DISCONTINUATION OF STUDY INTERVENTION

In case subject discontinues study intervention the hearing aids and other study material given are returned and the subject is out of the study. Organization of returned materials/hearing aids will be handled by the Sponsor in collaboration with site. No further follow up is necessary.

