7.2 SUBJECT DISCONTINUATION/WITHDRAWAL FROM THE STUDY

Subjects are free to withdraw from participation in the study at any time upon request.

An investigator may discontinue or withdraw a subject from the study for the following reasons:

- If the subject meets an exclusion criterion (either newly developed or not previously recognized) that precludes further study participation
- Subject is unable to do Field Test 1 and/or 2 under real-life conditions due to quarantine or social distancing due to COVID-19 pandemic.

The reason for subject discontinuation or withdrawal from the study will be recorded on the Study completion Case Report Form (eCRF). Subjects who signed the ICF and are randomized but do not receive the study intervention may be replaced. Subjects who signed the ICF, and are randomized and receive the study intervention, and subsequently withdraw, or are withdrawn or discontinued from the study, will be replaced if the minimum number of 24 subjects has yet to be enrolled.

All data is collected during use of the investigational device. In case a patient is withdrawn from the study there is no further data collection needed, except in the case the patient would report an adverse event which would be seen as at least possibly related to the treatment with the device. In this case the patient will be followed up until the event is resolved.

Data collected before withdrawal of consent will be kept in the study.

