3. Speech understanding,
4. Satisfaction

If the timing is inconvenient (e.g., driving a car), the subject can delay the response to the survey (reminder is given to not delay the response unduly, e.g., for more than 1 hour).

Phone calls (approximately after 3 days +3 days field testing) are scheduled with investigational staff. These calls are intended to ensure that all EMA data collection tools are functioning and subjects are reminded to report any adverse device effects (ADE) occurring during field use. The subject also has the possibility to call/e-mail the investigation staff when needed; however, to mitigate the potential for introducing bias through counselling of the self-fit group, any questions about the *Vibe SF* fitting strategy or how to use the device will not be answered by the investigational staff.

For the subjects who start in the HCP fit strategy group, based on complaints the subjects have about sound quality, the audiologist/HCP is able to invite the subject for an in-person fine-tuning visit and adjust the fitting on their *Silk 1X* as in a real-life HCP fitting (standard clinical care).

Subjects are asked to report any ADEs occurring during field use.

All communication with the HCP and/or investigation staff during the field tests will be documented and saved.

8.1.4 VISIT 2

Subjects return to the clinic after approximately two weeks Field Test 1 use. Subjects complete two questionnaires: the APHAB and the SSQ-12, to reflect their hearing experience aided with the Field Test 1 hearing aids. An HCP or assistant reads through the filled-out questionnaires with the subject to make sure everything is understood and filled out sufficiently.

Subjects are asked to report any ADEs occurring during field use.

Cross-over design:

The Field Test 1 HCP fit strategy subjects now cross over to the *Vibe SF* strategy group. Subjects independently fit their *Vibe SF* hearing aids bilaterally themselves using the *EasyFit* web application on the study smartphone. They are provided with the *Vibe SF* Safety and Maintenance Information, Quick-Start Guide and Quick-Start Card (see Appendix II). The HCP will not interfere or assist the subject with the self-fitting.

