8.1.7 VISIT 3 (ONLY FOR CROSS-OVER DESIGN)

At the final session after approximately 4 weeks of total field use with a 5-day washout period after two weeks of field use, each subject returns the hearing aids from their second field use test.

Subjects are asked to report any ADEs occurring during field use.

Subjects again complete two questionnaires: the APHAB and the SSQ-12, reflecting their hearing experience aided with the Field Test 2 hearing aids. An HCP or assistant reads through the filled-out questionnaires with the subject to make sure everything is understood and filled out sufficiently.

Effectiveness is measured with QuickSIN in an unaided condition and aided with the *Vibe SF* and Silk 1X HCP fit hearing aids in a sound attenuated booth. Aided testing will be conducted double-blinded and subject is given their field test 1 and 2 devices (*Vibe SF* and Silk 1X HCP fit hearing aids) in randomized order.

REM will be conducted double-blinded, and the subject is given field test 1 and 2 devices (*Vibe SF* & Silk 1X HCP fit hearing aids) in randomized order.

The subject will be asked to fill out a 5-point Likert scale to respond to the prompt: *Based on your listening experiences regarding speech understanding, sound quality and naturalness for both products, if you could keep one pair of these hearing aids, which pair would you choose: Greatly prefer A, Somewhat Prefer A, No Preference, Somewhat Prefer B, Greatly Prefer B.*

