9.4.1.3 IMPUTATION OF MISSING DATA AND SENSITIVITY ANALYSES

All attempts will be made to minimize missing data. However, if any subjects in the ITT population have missing primary endpoints, five (5) multiple imputations will be used for the analyses. This consists of imputing values for each missing value as a set (generating 5-sets), analyzing the results for each set, and then pooling the results. The Primary Effectiveness Endpoint is continuous, so the imputation method will be a multiple linear regression using treatment assignment and baseline characteristics.

Protocol #: D00232675

08 September 2021

A sensitivity analysis of the Primary Effectiveness Endpoint will be conducted as a tipping-point analysis, to examine the impact of missing data. It will only be conducted if the hypothesis test passes (i.e., rejects H_0). We will start by assuming that all missing Primary Effectiveness Endpoints have values indicating the inferiority of *Vibe SF* strategy, and if the Primary Effectiveness Hypothesis is not passed, we will change one missing endpoint to a difference of 0 until the hypothesis passes. This will enable determination of the amount of missing data that would alter the final result on the primary effectiveness endpoint.

If the hypothesis test of the Primary Effectiveness Endpoint does not pass, the hypothesis test will be repeated using only those subjects without major protocol violations, i.e., the mITT population. This test is for SPONSOR's information only, and will not be used to support the study objective.

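### No aided APHAB is taken for a device a subject gives up, so a self-fit failure is imputed in the primary ITT test like a Vibe SF completer with the same baseline

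*Combined protocol and SAP*

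**What the plan says.** Section 7.1: when a subject discontinues, "the hearing aids and other study material given are returned and the subject is out of the study", and "No further follow up is necessary". Section 7.2 says the same of withdrawal: "In case a patient is withdrawn from the study there is no further data collection needed", with an exception only for a possibly related adverse event. What is already in hand stays: "Data collected before withdrawal of consent will be kept in the study". The reason for stopping is recorded on the study completion form. A treated subject who leaves "will be replaced if the minimum number of 24 subjects has yet to be enrolled".

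The aided APHAB is scheduled at two points only. For the first device it is Visit 2 (8.1.4: "Subjects return to the clinic after approximately two weeks Field Test 1 use"). For the second it is Visit 3 (8.1.7: "reflecting their hearing experience aided with the Field Test 2 hearing aids"). Neither the Schedule of Activities nor Section 8 describes an APHAB at early termination.

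Section 9.3 defines ITT as everyone who received at least one fitting and uses it for the primary test. Section 9.4.1.3 applies "if any subjects in the ITT population have missing primary endpoints": five imputations by linear regression on treatment assignment and baseline characteristics. If the primary test passes, a tipping-point analysis follows. It starts with every missing endpoint set to a value indicating Vibe SF inferiority.

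**The concern.** The trial exists to find out whether self-fitting works. A subject who abandons Vibe SF because it does not work is direct evidence on that question, and the plan does not ask for that subject's score. The imputation model contains neither the reason for stopping nor any outcome observed before it. The imputed value is therefore drawn from the distribution of people who kept the device.

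For that subject the substitution favours non-inferiority. The net effect depends on the HCP-fit side, because an HCP-fit failure imputed as a typical HCP-fit user pushes the other way. The documents do not say how stopping will divide. Section 8.1.3 does make an imbalance plausible: staff will not answer questions about the Vibe SF fitting or its use, whereas an HCP-fit subject can be invited for in-person fine-tuning.

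**Working it through.** **Inputs.** From 9.2: EC margin 26; SD of the paired difference 34.4 at zero correlation (24.3 within a fitting strategy); one-sided alpha 0.05 per subscale; up to 15% drop-out, planned as 24 + 4, so 4/28 = 14.3%. By assumption, because the documents give no value: the gap between leavers and completers, the split of leavers by device, and a correlation of 0.5 as the alternative to 0.

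**The plan's own figure.** A paired non-inferiority t-test with true difference 0 has noncentrality margin/(SD/√n). For EC at n = 23 this is 26/(34.4/√23) = 26/7.17 = 3.62, giving power 0.96892. BN at 23 gives 0.96555 and RV at 22 gives 0.96942. All three match 9.2.

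**Hidden bias.** Let a leavers on Vibe SF and b on HCP fit each differ from completers by gap G in the direction unfavourable to the device they left. Imputation estimates the completers' mean, so the estimate is too favourable to Vibe SF by (a − b) × G/28.

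- 2 on Vibe SF, G = 26: 52/28 = 1.86 points.
- 4 on Vibe SF, G = 26: 104/28 = 3.71 points.

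In the second case, if the true mean over all 28 equals the margin of 26, completers average 26 − 3.71 = 22.29 and leavers 48.29.

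**Standard error.** Only observed scores carry information, so n = 28 − (a + b).

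- Correlation 0: 34.4/√26 = 6.75; 34.4/√24 = 7.02.
- Correlation 0.5: SD = √(2 × 24.3² × 0.5) = 24.3, so 24.3/√26 = 4.77; 24.3/√24 = 4.96.

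**Error for a subscale at its margin.** This is the noncentral-t probability of passing with noncentrality bias/SE. For 4 lost that is 3.71/7.02 = 0.53 or 3.71/4.96 = 0.75.

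| Leavers SF / HCP | Gap | Bias | Error, corr. 0 | Error, corr. 0.5 |
|---|---|---|---|---|
| 2 / 0 | 26 | 1.86 | 8.4% | 10.3% |
| 4 / 0 | 26 | 3.71 | 12.9% | 17.9% |
| 4 / 0 | 13 | 1.86 | 8.3% | 10.0% |
| 3 / 1 | 26 | 1.86 | 8.3% | 10.0% |
| 2 / 2 | 26 | 0 | 5.0% | 5.0% |

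**Check against real imputation.** A simulation used five imputations, regression on one baseline covariate and Rubin's rules, with 4 Vibe SF leavers whose own difference is 52 (completers 21.67, a gap of 30.3). It gave 12.9% error, against 14.8% by noncentral t. With the leavers' scores collected it gave about 4%. The table may therefore run slightly high. If leavers' own difference merely equals the margin while the overall mean is also at the margin, leavers and completers are alike and there is no inflation.

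**All three subscales.** Success needs all three to pass. With all three at their margins, 4 Vibe SF leavers, the 3.71-point bias on each, zero correlation between devices and an assumed 0.5 to 0.8 between subscales, the simulated joint false-pass rate is about 2-5%. It would be higher with positive correlation between devices, since the same bias is then larger relative to the standard error.

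**The case against.** **Direction.** A reader might infer that the primary test leans toward non-inferiority as a matter of course. The documents do not support that. Sections 7.2 and 7.3 also list withdrawal for quarantine, newly found exclusion criteria and loss to follow-up, none tied to a device. Treating all four allowed drop-outs as Vibe SF failures is the extreme case, and a 2/2 split leaves the error at 5%. This stands.

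**Size.** A reader might take 13-18% as the trial's false-positive rate. It is the error on one subscale. It becomes the trial's error only if that subscale sits at its margin and the other two pass almost surely. The gap is also severe: leavers at 48.29 are nearly twice the EC margin. Away from the margin little changes. With completers at 0 and leavers at 26, EC passes about 96% of the time with imputation and 95% with full data, and passing is correct because the true mean is 3.71. This also stands.

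**What is lost.** A reader might infer that leavers have no APHAB at all. The unaided score is kept, and so is the Visit 2 score if the stop comes in Field Test 2. Nor does multiple imputation assign every leaver the average; it draws around a prediction from baseline.

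**The tipping-point analysis.** It is aimed at this problem and deserves credit. But it runs only after a pass, gives no number for inferiority, has no decision rule and leaves the primary result unchanged. If inferiority means exactly the margin, it catches little: in the simulated case with leavers at 52 and the overall mean at the margin, that starting point still passed in 14% of runs.

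**The estimand.** The endpoint is benefit after 14 days' wear, a period chosen to allow acclimatization. A score after brief, unblinded use measures something slightly different. This is the best argument against the remedy, and the fix has to answer it.

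**Conclusion.** The concern holds in a conditional form. Sections 7.1, 7.2, 9.3 and 9.4.1.3 together lay down a rule under which a self-fit failure stays in the primary test but is imputed as a completer with the same baseline. The bias favours Vibe SF if its leavers are more numerous or fare worse than HCP-fit leavers, which is plausible but not documented.

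Under the stated assumptions (a 26-point gap, all leavers on Vibe SF, correlation 0 to 0.5), the error on a subscale at its margin rises from 5% to about 8-10% with 2 lost and 13-18% with 4 lost. It does not rise if leavers are balanced. With all three subscales at their margins and zero correlation between devices, the joint error with 4 lost is about 2-5%. These figures are for the cross-over; the same stopping and imputation rules apply if the trial switches to parallel arms. The change is worth making because it is cheap and obtains the scores, which no sensitivity analysis can do.

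**What to change.** - In 7.1, 7.2 and the Schedule of Activities, ask any subject who stops a device and has not withdrawn consent to complete the aided APHAB for that device when it is returned, in person or by phone.
- Record days of use, and link the stop reason already on the completion form to the device concerned.
- In 9.4.1.3, use that score in the primary ITT analysis and impute only what is still missing. After a stop in Field Test 1, the other device's score will still be missing.
- Add a sensitivity analysis that excludes scores from fewer than 14 days of use.

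**Cost.** Protocol wording, one questionnaire per leaver, and a phone call where the device comes back without a visit, since 7.1 says only that sponsor and site organise returns. The downside is that some scores will reflect short use; the added sensitivity analysis shows whether that matters. Nothing about the devices or their management changes.
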